11.2 Secondary Efficacy Analyses

The secondary endpoint of the proportion of subjects with complete clearance of all treatable MC at Week 8 will be analyzed in the same manner as the primary endpoint. A sensitivity analysis using the PP Population will be provided.

11.3 Exploratory Analyses

The exploratory endpoints based on the proportion of subjects achieving complete clearance or 75%, 90%, or 95% reductions will be analyzed in the same manner as the primary endpoint.

Since the within-household correlation is expected to be small and the change and percent change from Baseline in the number of treatable MC are exploratory, they will be analyzed using a repeated measures mixed model for the respective visits with the same covariates as the primary model together with visits and treatment by visit; an unstructured covariance matrix will be utilized. If the calculation of the percent change from baseline is influenced by outliers with calculated values >100%, then the influence of outliers will be avoided for analysis by censoring them so that all values were in the range of -100% to 100%. If the model fails to converge, then other correlation structures will be explored.

Since the within-household correlation is expected to be small and time to first complete clearance of all MC is exploratory, it will be analyzed using Kaplan-Meier methods. The number and percentage of subjects achieving complete clearance, number and percentage of censored subjects, and Kaplan-Meier estimates of first quartile, median, and third quartile will be summarized by treatment group. Differences in Kaplan-Meier curves between the treatments will be tested for significance using a stratified log-rank test.

The proportion of subjects with scarring and the proportion of subjects with keloid or hypertrophic scarring will be summarized descriptively at each visit.

The change from Baseline of the composite score from age-matched (at Baseline) DLQI/CDLQI will be summarized descriptively and separately for each questionnaire. The scoring algorithms are detailed in [Appendix A](#). The CDLQI will be examined in the following Week 12 response categories: complete clearance, 95% reduction in lesion counts, 90% reduction in lesion counts, and subjects who did not achieve complete clearance. Additionally, the changes from Baseline in the following subscales: Symptoms and Feelings, Daily Activities, Leisure, Work and School, Personal Relationships, and Treatment, for DLQI, and Symptoms and Feelings, Leisure, School or Holidays, Personal Relationships, Sleep, and Treatment, for CDLQI, and each question will be summarized descriptively.

The subject-reported spread of MC to household members not in the study will be summarized descriptively including a breakdown of whether or not there was any spread and then a breakdown of the amount of spread within the household at each visit at the household level.

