4. STUDY DESIGN AND PLAN

This is a Phase 3 multi-center, randomized, double-blind, vehicle-controlled, parallel group study to be conducted in approximately 340 subjects ≥ 6 months of age with MC. After obtaining informed consent/assent, subjects who satisfy entry criteria will be randomized to a 2:1 (active:vehicle) scheme. Subjects receiving current treatment for MC at the time of the Screening Visit will enter a washout period of up to 14 days prior to randomization. In the event no washout period is required, Screening and Baseline visit activities may be combined into a single visit. At randomization, subjects will be stratified into 4 strata corresponding to the cross-classification of household number of randomly assigned subjects (1 subject per household vs 2 subjects per household) and investigator type (dermatologist vs other). Households randomizing 2 subjects will receive the same treatment assignment for both subjects. Up to 2 subjects from the same household may be randomly assigned on the same day, if both individually meet all inclusion and exclusion criteria. For subjects in the same household, Screening can occur on different days; however, the baseline visit must occur on the same day.

Subjects or their caregivers will apply SB206 12% or Vehicle Gel QD for a minimum of 4 weeks and up to 12 weeks to all lesions identified at Baseline and new treatable lesions that arise during the course of the study. Subjects or their caregivers will continue to treat the area until the next scheduled visit even if the lesion(s) clear. If the investigator determines all lesions are cleared at a clinic visit, the treatment may stop. At Weeks 2, 4, 8 and 12, the investigator will count and record the number of active (raised, treatable) molluscum lesions per body area. At Weeks 2, 4,

and 8, the investigator will determine if new lesions have occurred since the last visit, and the subject or caregiver will be instructed by the investigator to re-initiate treatment. If treatment is stopped due to clearance, subjects will continue regularly scheduled visits through Week 24.

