5. DETERMINATION OF SAMPLE SIZE

Approximately 340 subjects, 6 months of age and older, with a minimum of 3 and a maximum of 70 MC lesions at Baseline will be randomized in a 2:1 (active:vehicle) scheme. The sample size assumptions for this study were informed by the completed Phase 2 study NI-MC201 of subjects 2 years of age and older with between 3 and 70 MC lesions at Baseline. In the Intent-to-Treat (ITT) Population of the Phase 2 study, the observed rates of complete clearance at Week 12 were 18% (12/66) for vehicle and 38% (18/48) for SB206 12% QD and the covariate-adjusted treatment difference was 18%.

A sample size of 340 subjects (227 subjects in the SB206 12% QD group and 113 subjects in the vehicle group) will provide 94% power for a 2-sided alpha test of size 0.05 to detect an absolute difference of 18% when the vehicle response rate is 18%. This same sample size provides 93% power to detect a treatment difference of 18% when the vehicle response rate is 20% and 83% power when the treatment difference is 15% and the vehicle response rate is 20%.

Since the intra-cluster correlation is estimated to be small (<10%) and the average size of households is expected to be capped at roughly 1.3, the sample size is still sufficient when considering the fact that the subjects within the household may not be independent.

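### The exploratory mixed models and log-rank test ignore household clustering although treatment is assigned by household; at the SAP's own limits the effect is slight, and a household-robust variance would remove it

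*Combined protocol and SAP*

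**What the plan says.** References are to the most recent SAP in the file.

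- **Allocation.** SAP 4 states: "Households randomizing 2 subjects will receive the same treatment assignment for both subjects". It also states "Up to 2 subjects from the same household may be randomly assigned on the same day", so a cluster holds one or two subjects.
- **Analyses that cluster.** SAP 11.1 fits the primary model as a GEE with household ID as the cluster and an exchangeable working correlation. SAP 11.2 uses the same model for the Week 8 endpoint. SAP 11.3 uses it for the exploratory clearance and 75%, 90% and 95% reduction endpoints.
- **Analyses that do not.** For change and percent change in lesion count, SAP 11.3 says "they will be analyzed using a repeated measures mixed model for the respective visits with the same covariates as the primary model", with visit, treatment by visit and an unstructured covariance. For time to clearance it plans Kaplan-Meier summaries and a stratified log-rank test whose strata are not named. Neither has a household random effect or a household-robust variance. The stated reason for the second is "Since the within-household correlation is expected to be small and time to first complete clearance of all MC is exploratory"; the first carries the same two-part reason.
- **Size of the clustering.** SAP 5 puts the intra-cluster correlation (ICC) below 10% and adds that "the average size of households is expected to be capped at roughly 1.3". No source is given for either figure.
- **Status of the p-values.** The protocol synopsis makes exploratory p-values nominal. SAP 10.7 confines the fixed sequence to the primary and secondary endpoints.

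**The concern.** The unit of allocation is the household, so a test that counts the two members of a pair as independent credits the trial with more information than it has whenever their outcomes are positively correlated. Household number is a covariate in the mixed models, but that adjusts the mean and leaves the within-pair correlation in place. Stratifying the log-rank test by the randomization factors would not remove it either.

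The SAP accepts this on the ground that the correlation should be small. The only figure for it stands in the sample-size section, which concerns complete clearance at Week 12. Nothing links that figure to lesion-count change or to time to clearance.

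At stake is how these exploratory comparisons are read. SAP 6 declares tests significant at p ≤ 0.05 unless otherwise noted, and SAP 11.3 says the Kaplan-Meier curves will be tested for significance.

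**Working it through.** **1. The plan's own power.** Inputs from SAP 5: 227 and 113 subjects, two-sided alpha 0.05, 36% versus 18%. With a pooled-variance z-test:
- pooled rate = (227 × 0.36 + 113 × 0.18)/340 = 0.300
- SE under the null = √[0.300 × 0.700 × (1/227 + 1/113)] = 0.0528
- SE under the alternative = √[0.36 × 0.64/227 + 0.18 × 0.82/113] = 0.0482
- power = Φ[(0.18 − 1.96 × 0.0528)/0.0482] = 94.4%

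The other two scenarios give 93.4% and 82.8%. All three agree with the stated 94%, 93% and 83%, so the stated power treats subjects as independent.

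**2. Household mix.** With sizes 1 and 2 and a mean of 1.3, 30% of households are pairs. Then E[m²] = 0.7 × 1 + 0.3 × 4 = 1.9, and 0.6/1.3 = 46% of subjects are in pairs.

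**3. Design effect when both members share an arm.** DE = 1 + (E[m²]/E[m] − 1) × ICC = 1 + (1.9/1.3 − 1) × ICC = 1 + 0.4615 × ICC. The correct SE is √DE times the naive one. The true two-sided error of a nominal 5% test is 2 × [1 − Φ(1.96/√DE)].

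**4. Results at mean household size 1.3.** The simulation used 184 single and 78 paired households (340 subjects), 2:1 allocation by household and 20,000 runs. It fitted a linear model at one time point with household number as covariate, and a log-rank test stratified by household number. Both ignored clustering.

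| ICC | DE | √DE | True error, formula | Simulated, linear | Simulated, log-rank |
|---|---|---|---|---|---|
| 0 | 1 | 1 | 5.0% | 5.2% | 5.3% |
| 0.05 | 1.023 | 1.011 | 5.3% | – | – |
| 0.10 (SAP bound) | 1.046 | 1.023 | 5.5% | 5.6% | 5.6% |
| 0.20 (assumed) | 1.092 | 1.045 | 6.1% | – | – |
| 0.30 (assumed) | 1.138 | 1.067 | 6.6% | 7.0% | 6.2% |
| 0.50 (assumed) | 1.231 | 1.109 | 7.7% | 7.8% | 6.9% |
| 1 (ceiling) | 1.462 | 1.209 | 10.5% | – | – |

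The Monte Carlo error of a 5% rate over 20,000 runs is √(0.05 × 0.95/20,000) = 0.15 points. At the SAP's bound, clustering adds 0.3 to 0.4 points to the simulated error at ICC 0. For the log-rank test the formula is somewhat too high at the larger ICCs.

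**5. What this does to a p-value.** At ICC 0.10 a reported p of 0.040 (z = 2.054) becomes z = 2.054/1.023 = 2.008, or p = 0.045.

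**6. If the household mean is larger (assumed).** At ICC 0.10, a mean of 1.5 gives DE 1.067 and a true error of 5.8%. All households paired gives DE 1.10 and 6.2%.

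**The case against.** The case for leaving the plan alone is strong on size. The SAP discloses the simplification and gives two reasons for it. Its ICC and household size are both upper limits, so 5.5% is roughly a ceiling under the plan and not a central value. Clustering is handled for the primary, secondary and responder-type endpoints, and SAP 11.1 adds a one-subject-per-household sensitivity analysis for the primary. The primary GEE will also estimate a within-household correlation for clearance, which is a partial check on the assumption. Finally, about 70% of households are single, so a household random intercept is identified only from the pairs, and SAP 11.3 already foresees that the simpler model may not converge.

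All of that stands and limits the point. Two things do not. Exploratory status is not applied consistently, since other exploratory endpoints in the same section do get the household GEE. And the small expected correlation is asserted without a source for these outcomes.

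A reader might infer more than the documents support:
- **That the standard errors are certainly too small.** This needs a positive ICC for these endpoints, which is unknown. The protocol's background reports transmission to other children in the household in 41% of cases. That makes positive correlation plausible but is no estimate of correlation in response.
- **That correlation shrinks the standard error.** It raises the true standard error; the naive estimate fails to follow.
- **That shared treatment is a source of the correlation.** Arm is the comparison itself, so it leaves no residual correlation. A shared virus or caregiver could, but that is inference.
- **That the trial's type I error is compromised, or that every exploratory test ignores households.** Neither is so, given SAP 10.7 and the GEE analyses.

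**Conclusion.** The point holds as a minor one. The mixed models and the log-rank test do not match the unit of allocation, and they understate uncertainty if the within-household correlation is positive. Taking ICC 0.10 and mean household size 1.3 as limits, the correct standard error is at most about 2.3% larger than the naive one, and the true error is about 5.5% where 5% is claimed. By the formula, the error passes 6% at mean size 1.3 only from an ICC of about 0.2, twice the SAP's bound. ICCs above 0.10, household means above 1.3 and the simulated clearance-time distribution are assumptions, not figures from the documents. The simulated linear model had one time point, so it stands in for the repeated-measures model only approximately. This is a disclosed choice that can be improved; it is not a threat to the trial's confirmatory conclusions.

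**What to change.** In SAP 11.3, before unblinding:

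- **Change and percent change.** Use a household-level sandwich variance, or add a household random intercept. If the random intercept does not converge, fall back on the sandwich variance.
- **Time to clearance.** Compare arms with a score or Wald test from a stratified Cox model, using a robust variance aggregated by household. Keep the Kaplan-Meier summaries, and name the strata.

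No new data are needed, because household ID is already in the primary model. The cost is SAP wording, some model specification, slightly wider intervals under positive correlation, and a change of named test for one exploratory endpoint. In return the tests no longer rest on an unsourced ICC; if the correlation is as small as expected, the results will barely move.

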12. OTHER ANALYSES

The following analyses of BOTE vs lesion count/complete clearance will be presented:

- Percent change from Baseline at Week 12 in relation to the highest BOTE score during treatment.
- Complete clearance at Week 12 in relation to the highest BOTE score during treatment.

- Percent change from Baseline at each visit in relation to BOTE score at Week 2.
- Complete clearance at each visit in relation to BOTE score at Week 2.

In these analyses, the BOTE scores will be analyzed in the ITT Population as follows:

1. Dichotomized:

- a. Score of 0 or 1: No to Mild
- b. Score of 2, 3, or 4: Moderate to Very Severe

A shift table comparing the baseline BOTE score to each scheduled postbaseline assessment will be presented for the Safety Population.

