Inflammatory reactions around the MC has been associated with imminent resolution of MC (sometimes referred to as “beginning-of-the-end” [“BOTE”] sign). The investigator (or designated evaluator) will assess the presence and overall degree of inflammatory reactions at MC lesions at Baseline (before dosing) and Weeks 2 through 12. In most cases, clinical features can differentiate between BOTE and LSR. BOTE may be associated with itch, but not pain. BOTE is usually asymptomatic, self-limited, and localized to individual MC lesions and does not require discontinuation of study treatment or additional treatment. LSR is generally more diffuse, associated with significant itch or tenderness, may necessitate discontinuation of study treatment, and may need treatment for symptomatic relief (e.g., a topical corticosteroid or topical anesthetic). For very severe LSR, systemic corticosteroids may be considered. Investigators will assess the treatment area at each scheduled visit and use their medical judgement to differentiate between BOTE and LSRs. BOTE Inflammation Score and LSR score will be recorded at each visit. BOTE should not be considered an AE. When LSRs are clinically significant at the application site, the investigator should report the condition as an AE(s).

At Baseline (at least 30 minutes after dosing) and Weeks 2 through 12, the investigators will rate LSRs on individual features including erythema, flaking/scaling, crusting, swelling, vesiculation/pustulation, and erosion/ulceration. At Baseline (pre-dose) and Weeks 2 through 12, the investigators will rate BOTE signs using the BOTE Inflammation Score.

The following tables describe the scoring parameters for the BOTE Inflammation Score and LSR score.

BOTE Inflammation Score

Score	Global Assessment	Description
0	No inflammation	No evidence of local inflammation
1	Mild	Minimal erythema and/or edema
2	Moderate	Definite erythema and/or edema with or without hemorrhagic crusting
3	Severe	Erythema and edema with definite hemorrhagic crusting
4	Very severe	Strong reaction spreading beyond the treated area, bullous reaction, erosions

LSR Score

Score	Erythema	Flaking/ Scaling	Crusting	Swelling	Vesiculation/ Pustulation	Erosion/ Ulceration
0	Not present	Not present	Not present	Not present	Not present	Not present
1	Slightly pink	Mild, limited	Isolated crusting	Minimal, limited	Fine vesicles	Superficial erosion

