The study treatment period is defined from randomization through completion of Week 12/ET1 visit and the safety follow-up period is from the completion of Week 12 through the completion of Week 24/ET2 visit.

After all subjects have completed their Week 12/ET1 visit, thus completing the Treatment Period of the study, the database through Week 12/ET1 will be frozen and unblinded for purposes of the primary analysis of efficacy and safety. While this analysis is being prepared, the subjects will continue through Week 24/ET2. After all subjects have completed their Week 24/ET2 visit, the database will be locked and the follow-up data will be analyzed.

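### Final SAP section 12 relates Week 12 outcomes to the highest BOTE score during treatment, an exposure that depends on clearance and dropout, so the association is biased in an unknown direction

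*Combined protocol and SAP*

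**What the plan says.** Final SAP section 12 (Other Analyses) lists two summaries built on a maximum: "Complete clearance at Week 12 in relation to the highest BOTE score during treatment" and "Percent change from Baseline at Week 12 in relation to the highest BOTE score during treatment". Both use the ITT population, with BOTE split into 0–1 and 2–4. They feed Table 14.2.3.10.1 and Figure 14.2.3.10.2. The same section relates the Week 2 BOTE score to percent change and clearance at each visit (Tables 14.2.3.10.3 and 14.2.3.10.4).

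The window is set in final SAP section 6: "The study treatment period is defined from randomization through completion of Week 12/ET1 visit". The protocol's Schedule of Assessments (footnote 4) has BOTE scored at Visits 3 to 6, that is Weeks 2, 4, 8 and 12, after the pre-dose score at Baseline.

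On what is scored, final SAP section 4 says the investigator or designated evaluator "will assess the presence and overall degree of inflammatory reactions at MC lesions". It also says "BOTE Inflammation Score and LSR score will be recorded at each visit" and "Investigators will assess the treatment area at each scheduled visit and use their medical judgement to differentiate between BOTE and LSRs". For subjects who clear early: "If treatment is stopped due to clearance, subjects will continue regularly scheduled visits through Week 24". A missing response counts as non-response (final SAP section 10.4). Section 12 gives no landmark, no limit to visits before clearance, and no rule for scoring BOTE in a lesion-free subject or one with missed visits.

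**The concern.** Protocol and SAP describe BOTE as inflammation that tends to appear when lesions are about to resolve, and this table and figure will be read as evidence on that. For such a reading the exposure should be complete before the outcome is observed, and every subject should have had the same opportunity to be exposed. Neither holds here. The Week 12 score enters the maximum and is taken at the visit that defines the outcome. If BOTE needs a lesion, a subject first clear at Week 4 has had one scoring visit with lesions (Week 2), one first clear at Week 8 has had two, and one who never clears has had four. Subjects who leave early are non-responders with few scores, which works in the opposite direction. The maximum thus partly records how long lesions persisted and how long the subject stayed, and that information overlaps with the outcome.

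**Working it through.** The plan gives no figure for this analysis, so there is nothing to reproduce. The check asks what odds ratio (OR) the planned table would show if BOTE and clearance were unrelated.

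**From the documents.** Four post-baseline BOTE visits; the cut at 2; a 36% Week 12 clearance rate on SB206 (18% vehicle plus an 18-point difference, final SAP section 5); dropouts counted as non-responders.

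**Assumed.** Probability q of BOTE 2 or more at a visit with lesions: 0.1, 0.2 or 0.3. First clearance at Weeks 2/4/8/12 in 1/6/13/16% of subjects (timing A) or 0/3/11/22% (timing B), each summing to 36%. Clearers stay clear.

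**Case 1: clear skin scores 0, no dropout.**

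- Non-clearer: P(high) = 1 − (1 − q)^4.
- Clearer: P(high) = average of 1 − (1 − q)^k, with k = 0, 1, 2, 3 for first clearance at Weeks 2, 4, 8, 12.
- OR = odds of high among clearers / odds of high among non-clearers.

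With q = 0.2 and timing A:

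- Non-clearers: 1 − 0.8^4 = 0.590.
- Clearers: (0.01×0 + 0.06×0.2 + 0.13×0.36 + 0.16×0.488)/0.36 = 0.1369/0.36 = 0.380.
- Clearance if highest BOTE is 2 or more: 0.36×0.380/(0.36×0.380 + 0.64×0.590) = 26.6%.
- Clearance if it is below 2: 0.36×0.620/(0.36×0.620 + 0.64×0.410) = 46.0%.
- OR = (0.380/0.620)/(0.590/0.410) = 0.43.

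| Timing | q = 0.1 | q = 0.2 | q = 0.3 |
|---|---|---|---|
| A | 0.49 | 0.43 | 0.35 |
| B | 0.58 | 0.51 | 0.44 |

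The true OR is 1 in every cell. The formula depends on the timing mix, not on the overall clearance rate. Dropping only the Week 12 score leaves 0.70, 0.64 and 0.58 for timing A, so the overlap with the outcome visit is only part of the problem.

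**Case 2: the treatment area is still scored after clearance, at the same rate q** (q = 0.2). Without dropout, everyone has four chances and the OR is 1.00. Now let a share d of non-responders be dropouts with one score:

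- d = 15%: non-responders 0.85×0.590 + 0.15×0.2 = 0.532; OR = (0.590/0.410)/(0.532/0.468) = 1.27.
- d = 30%: non-responders 0.70×0.590 + 0.30×0.2 = 0.473; OR = (0.590/0.410)/(0.473/0.527) = 1.60.

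**Between the two.** Scoring after clearance at half the rate, with 30% dropout among non-responders, gives 1.08.

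**With a real effect.** In a simulation of the four visits (36% clearance, clear skin scoring 0, q from 0.1 to 0.3), BOTE multiplied the odds of clearing by the next visit. Without dropout, a factor of 3 appeared as an OR of 0.72 to 0.91, a factor of 5 as 1.08 to 1.29, and a factor of 8 as 1.56 to 1.79. A factor of 3 with 8% dropout per visit appeared as 1.25 to 1.35.

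**Landmark.** In the same simulation with no true effect and no dropout, Week 2 BOTE among subjects not yet clear, against Week 12 clearance, gave 0.97 to 1.03.

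**The case against.** Case 1 rests on reading BOTE as impossible once lesions are gone, and the documents do not say that. Scores are recorded at every visit, the treatment area is examined, the score levels describe redness, swelling and crusting, and visits continue after clearance. Protocol section 7.1.1 allows residual surface changes on skin that counts as clear. This stands, and it has a consequence: a reader might infer that the table is bound to show a false negative association, and the documents do not support that. The sign turns on post-clearance scoring and dropout, neither of which they give.

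A reader might also infer that a true positive association would always be hidden or reversed. The simulation shows a moderate effect can be reversed, while stronger effects, or a moderate one with dropout, still show as positive.

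Nor is this table the trial's test of BOTE. No test is specified, BOTE is not part of any efficacy endpoint, and the same section plans the Week 2 BOTE analyses, which fix the exposure early and largely avoid the problem. They do not avoid it fully, because they keep subjects already clear at Week 2 and include Week 2 itself as an outcome visit.

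The table shells and dataset specifications are separate files and may define the maximum more narrowly. The SAP text does not.

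**Conclusion.** The point holds as one of bias with unknown direction. The maximum covers the outcome visit, and the opportunity to reach it depends on clearance and dropout; nothing in the SAP corrects for either. With no true association, the planned table would show an OR of about 0.35 to 0.58 if clear skin scores 0 and nobody drops out. It could show 1.27 to 1.60 if scoring continues after clearance and 15% to 30% of non-responders leave after one score. These figures rest on assumed BOTE rates, clearance timing and dropout, so they show the possible size and do not predict the result. The table and figure cannot be read as evidence for or against BOTE as a sign of resolution. No primary or secondary conclusion is affected, and the priority is low.

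**What to change.** In section 12, replace the highest score during treatment with a landmark exposure: the highest BOTE at Weeks 2 and 4, among subjects still in the study with a lesion count above 0 at Week 4, against clearance and percent change at Week 12. In the Week 2 BOTE analyses, include only subjects not clear at Week 2 and use outcomes at Weeks 4, 8 and 12. Update Tables 14.2.3.10.1, 14.2.3.10.3 and 14.2.3.10.4 and Figure 14.2.3.10.2 to match.

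The cost is a change of SAP wording and the reprogramming of three tables and one figure, with no new data. Subjects who clear or leave by Week 4 drop out of the landmark table, including any whose Week 2 inflammation was followed by clearance at Week 4, and the Week 8 BOTE score is not used.
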